7.3.4. Adverse events Step 2 only OBSP

Objective: To compare the safety of CAB LA vs. oral TDF/FTC proximal to blinded study drug administration

Population: Step 2 safety

Censoring: AEs are censored using ON BLINDED STUDY PRODUCT (OBSP) censoring.

Details of the OBSP censoring definitions are given in Appendix B. Reported AEs will be excluded if they occur before the first injection or after the OBSP censoring time.

Descriptive and Statistical Analysis will be performed as above

7.3.5. *Laboratory evaluations*

Population: Primary Safety

Descriptive: Laboratory findings for CBC, chemistries (urea, creatinine, CPK, glucose, calcium, phosphorous, amylase, lipase), liver function (AST, ALT, total bilirubin, alkaline phosphatase) and fasting lipid profile (total cholesterol, triglycerides, HDL, LDL) will be reported by grade, as defined in the “Division of AIDS (DAIDS) Table for Grading the Severity of Adult and Pediatric Adverse Events”. The proportion of laboratory findings qualifying as Grade 2 or above will be presented. Laboratory values will be reported by arm as median, 1st and 3rd quartiles, min and max, and (at follow-up visits) as median, 1st and 3rd quartile change from baseline (see below). Summaries involving values and changes from baseline at scheduled visit time points will consider values from scheduled visits only, and in the case of missing values, results will not be carried forward from interim (unscheduled) visits. For summaries and analyses involving changes in laboratory values over time or maximum change from baseline (e.g. shift tables), values from interim (unscheduled) visits will also be considered.

Formal comparisons of laboratory values will be conducted as follows:

- Absolute values: A mixed-effects model with participant as the random effect and site and arm as fixed effects will be used to assess overall differences in each laboratory outcome by arm. Outcomes with highly skewed distributions will be log-transformed. A continuous time (elapsed study time) term and an interaction of time with study arm will be added to model time trends in laboratory values that may emerge with continuous exposure to study drug. Only post baseline visits will be included.
- Change from baseline. A fixed effect model with site and arm as covariates will be used to assess overall change from baseline for each laboratory outcome by arm. A continuous time (elapsed study time) term and an interaction of time with study arm will be added to model differences in laboratory values that may emerge with continuous exposure to study drug.

Note: Formal comparisons of laboratory values as described above will not be included in the Clinical Study Report.

7.3.6. *Secondary Analyses*

- a. **Objective:** To compare HIV incidence among participants receiving oral CAB/CAB LA vs. daily oral TDF/FTC (Steps 1, 2 and 3).

Population: mITT population

Outcome: Time of HIV-1 Infection

This analysis will be similar to the primary analysis of HIV incidence but will include the entire follow-up period (steps 1, 2 and 3) for each participant. The analysis will be based on a Cox model using time to HIV detection (as defined in the primary analysis) as the outcome. The model will include an indicator for intervention arm (TDF/FTC = 0; CAB LA = 1) and be stratified by site. Participants who remain HIV-1 uninfected will be censored at their last negative HIV test. A formal statistical comparison between study arms will be performed using a Wald test of the hypothesis

Ho: HR = 1

Ha: HR < 1

A one-sided test with $\alpha = .025$ will be used. The estimated hazard ratio (HR), a 95% confidence interval, and a p-value for the hypothesis shown above will be given.

b. **Objective:** To evaluate relative efficacy of oral CAB/CAB LA vs. oral TDF/FTC in subgroups defined by the baseline factors of age, herpes simplex virus-2 (HSV-2) serostatus, and body mass index (BMI).

Population: mITT population

Outcome: Time of HIV-1 Infection

These analyses will be similar to the primary analysis of HIV incidence and will include data from follow-up steps 1 and 2 for each participant. The number of events, person-years and incidence will be calculated for each arm within each subgroup.

Subgroups will be defined as follows:

Age (<25 vs ≥ 25)

HSV-2(positive or negative)

BMI (<30.0 vs ≥ 30.0)

Contraceptive method during treatment (DMPA, Net_EN, Implants, Other)

Age, HSV-2 and BMI will be based on baseline status while contraception will be treated as a time-varying covariate.

The analyses of efficacy will be based on a Cox model using time to HIV detection (as defined in the primary analysis) as the outcome. Separate models will be fit for each of the three baseline covariates of interest. Each model will be stratified by site and will include an indicator for intervention arm (TDF/FTC = 0; CAB LA = 1), the covariate of interest and their interaction.

A formal statistical comparison of efficacy between the subgroups will be performed using a Wald test of the hypothesis

Ho: interaction term = 0

Ha: interaction term $\neq 0$

A two-sided test with $\alpha = .05$ will be used.

The efficacy (relative hazard) of CAB LA versus TDF/FTC and 95% CI will be calculated for each subgroup using standard methods for linear combinations of the Cox model coefficients.

c. **Objective:** To describe and model the relationship between HIV incidence and drug concentration, within each arm.

Population: PK analysis population

Outcome: Time of HIV-1 Infection

These analyses will include data from follow-up steps 1 and 2 for each participant in the PK analysis population. Separate analyses will be conducted for each arm. The analyses will be based on a logistic regression of all available intervals with drug concentration/PK parameter data. The outcome will be HIV infection (yes/no) as measured at the end of the interval. For each arm, the drug concentration/ PK parameter of interest in each interval will be determined in conjunction with colleagues from the central lab and ViiV (see separate document with more details on the PK study design). A plot of the model predicted relative hazard of HIV infection (y-axis) versus drug concentration (x-axis) with a 95% confidence interval will be generated from the final model.

d. **Objective:** To describe the distribution and correlates of drug concentration, within each arm.

Population: PK analysis population

Endpoint: Drug concentration

These analyses will include data from follow-up steps 1 and 2 for each participant. Separate analyses will be conducted for each arm.

Descriptive analyses: A histogram of all measured drug concentrations/PK parameter estimates will be generated. Boxplots of these outcomes will be generated both overall, over time and for key subgroups (age, HSV-2 serostatus, BMI, reported/documentad adherence).

Statistical Analyses: Multiple linear regression analyses with correction for correlated data and robust variances (i.e. generalized estimating equations) will be used to relate log of the drug concentration to age, HSV-2 serostatus, BMI and any other covariates of interest. Reported (oral pills) or documented (injection) level of adherence will be included in the models. The coefficient of each covariate and a 95% confidence interval will be provided.

e. **Objective:** To compare the acceptability of and preferences for CAB LA vs. oral TDF/FTC.

Population: mITT population

Outcomes: Two primary outcome variables will be used:

- Response to CASI question (step 3, day 0, visit 33.0) "If you wanted to protect yourself from getting HIV, which of the following product(s) would you prefer to use?"
- Response to (Likert-scale) CASI questions (step 3, day 0, visit 33.0) i) "How often do you find it inconvenient or difficult to take your oral study medication (i.e. the tablets) as recommended?" ii) "How often do you find it inconvenient or difficult to receive your injection as recommended?"

Descriptive analysis: Responses to these questions will be summarized by arm for the CSR.

Statistical Analysis: The CSR will only display descriptive summaries as described above. Subsequent analyses will be conducted on data collected at the end of step 2 (visit 33.0). Chi-square tests and Fisher-exact tests will be used as appropriate, with Likert scales converted to Binary by distributions within the response levels (e.g. at the median response). Inference for differences by arm will be analyzed using logistic regression models. Each model will contain two terms:

- Country
- Randomized study arm.

7.3.7. *Tertiary Analyses*

a. **Objective:** To estimate sexual risk behaviors, as measured by self-report and rates of incident sexually transmitted infections (STIs).

Population: mITT population

Outcomes:

- i. Sexual risk
 - Any condomless sex with an HIV-infected or HIV-unknown status partner
 - >1 sexual partners in past 1 months
- ii. Incident STIs (measured at weeks 33, 57, 81, 105, 129, 153 and 177 during Step 2, and weeks 24 and 48 during Step 3)
 - Time to incident STI (any of Gonorrhea, Chlamydia, Syphilis)

Analysis: Data from steps 1, 2 and 3 will be used unless indicated otherwise.

The proportion of participants reporting any high-risk behavior will be assessed at each visit. Mixed effects logistic regression will be used to estimate prevalence and 95% confidence intervals for each behavior. Time trends during follow-up will be estimated using mixed effects logistic regression. Linear and non-linear models (with respect to time) will be explored.

Rates of incident STI's will be computed as number of new STI's divided by total person-years. Poisson regression with a robust variance will be used to model the number of incidents STI for each woman. Person-time will be used as an offset. Incidence and a 95% CI will be reported overall and by arm.

b. **Objective:** To compare Grade >2 adverse event (AE) rates in women with baseline BMI $</\geq 25$ kg/m², within each study arm.

Population: Primary Safety Population

Outcome: Counts of grade 2 or higher AE

For each arm, tables will summarize the number of grade 2 or higher AEs by MedDRA System Organ Class and BMI. Participant with multiple AEs within a category will be counted once under the maximum severity. The overall grade 2 or higher event rate and a 95% confidence interval will be calculated for those with BMI $<$ and ≥ 30 kg/m² at baseline based on a log-linear model for counts using log(person-time) as an offset, assuming a Poisson distribution, and using a robust variance (i.e. generalized estimating equations). Event rates will be compared between those with BMI $<$ and ≥ 30 kg/m² at baseline using a similar model.

c. **Objective:** To compare differences in weight gain, by arm.

Population: Primary Safety Population

Outcome: Weight (kg)

Weight gain will be computed as change from baseline (enrollment) at each follow-up visit. We will plot mean weight gain over follow-up by treatment arm. A linear mixed model with random person and time effects will be fit with (i) continuous time and (ii) categorical intervals for time in study, treatment and time by treatment interaction to evaluate the effect of CAB LA on weight gain. The interaction between time and treatment will quantify the difference in weight gain by arm. A second analysis that removes women when they become pregnant will be conducted.

d. **Objective:** To compare pregnancy incidence and outcomes between arms.

Population: mITT Population and PREGNANCY Subgroup Population

Outcome: New pregnancies and pregnancy outcomes

Data from steps 1 and 2 (PRIMARY mITT dataset) will be used. Tables will summarize the number of pregnancies and pregnancy rate by arm. The pregnancy rate and 95% robust confidence interval for each treatment arm will be calculated using a log-linear model for counts using log(person-time) (excluding time spent pregnant) as an offset, assuming a Poisson distribution, and using a robust variance (i.e. generalized estimating equations).

Outcomes of all detected pregnancies (PREGNANCY dataset) and all confirmed pregnancies (CONFIRMED PREGNANCY dataset), including information of drug exposure during the conception period and pregnancy period, will be tabulated by arm.

e. **Objective:** To evaluate rates of HIV drug resistance among participants who acquire HIV infection during the study among participants receiving oral CAB/CAB LA vs. oral TDF/FTC.

Population: Primary SEROCONVERTER Population

Data from steps 1, 2 and 3 will be included. The number of cases of drug resistance will be summarized by arm and step. All cases of drug resistance among incident HIV infections during the study will be described.

f. **Objective:** To determine plasma concentrations of medroxyprogesterone (DMPA) or norethisterone (NET-EN) or etonorgestrel (from implants) when co-administered with CAB LA.

Population: CONTRACEPTION Subgroup Population

Outcome: Plasma concentration of medroxyprogesterone or norethisterone.

Boxplots of plasma concentrations of DMPA/NET_EN/etonorgestrel will be generated by arm. For women in the CAB-LA arm, a plot of plasma concentrations versus time since last injection will be plotted and a smooth line will be fit through the data. Proportion of women with plasma concentrations below 0.1 ng/mL (DMPA) or TBD (NET_EN) or 90pg/mL (etonorgestrel) will be reported and compared (separately, for women using each drug) between arms using a Fisher's exact test or a permutation test if multiple observations are available on each woman.

In addition, we will compare mean contraceptive drug levels (and/or other PK parameters) between the CAB LA and TDF/FTC arms for each contraceptive subgroup using a t-test (or a t-test with robust variance if multiple observations on each woman are available).

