6.5 Injection (Step 2) Efficacy Population

The mITT population who receive at least one injection and are uninfected at the time of the first injection, and had at least one follow-up visit with HIV status determined after the first injection.

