
Ho: HR = 1

Ha: HR < 1

A two-sided test with $\alpha = .05$ will be used. The estimated hazard ratio (HR), a 95% confidence interval, and a p-value for the hypothesis shown above will be given. If the number of events is small (<40) then the p-value will be confirmed using a permutation test based on 100,000 random permutations of the treatment assignments; if there is a meaningful difference between the permutation and asymptotic procedures, the permutation p-value will be used. Treatment efficacy will be estimated as $TE = 1 - HR$.

If the trial is stopped early (prior to the final analysis), then the primary results will be reported as a bias-adjusted mean HR and design-adjusted 95% CI (Emerson S and Fleming TR. Symmetric Group Sequential Test Designs. *Biometrics* 45:904-923, 1989).

7.3.1.1. Sensitivity of the Primary mITT results:

The following sensitivity analyses are proposed to aid in interpretation of the primary ITT results :

- A per-protocol analysis, excluding participants with exclusionary protocol violations, will be conducted if the number of participants affected exceeds 2% of the enrolled population.
Population: Per Protocol
This analysis will be identical to the mITT analysis, except that for partial exclusions, the follow-up will be censored on the last non-missing HIV test result date on or prior to the date of the deviation that resulted in exclusion from the per-protocol population.
- A supportive analysis will be presented using the OBSP censoring in the Injection (Step 2) Efficacy population (see OBSP censoring definitions in appendix B), where study follow-up is censored when a participant does not receive blinded injection study product on time.
- In this active control trial, the superiority of CAB LA is predicated in part on incomplete adherence to daily oral TDF/FTC. Specifically, we assume that overall adherence to TDF/FTC will be less than 50%. If adherence to TDF/FTC is high (greater than 50%) then, as described in section 7.8.4 of the protocol, a supportive non-inferiority (NI) analysis of CAB LA versus TDF/FTC may provide valuable information for interpreting the trial results.

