7.3.2. Primary Safety Analysis

Objective: To evaluate the relative safety of oral CAB/CAB LA (oral run-in and injections, Steps 1 and 2) vs. daily oral TDF/FTC for HIV prevention (Steps 1 and 2).

Population: Safety population

The primary pre-specified safety comparison between arms will be based on all AEs with maximum grade ≥ 2 . In general, formal statistical comparison of individual types of safety events across arms is not planned since interpretation of differences must rely heavily upon clinical judgment. Where formal statistical testing is considered necessary to guide judgement of observed differences for any single event or collection of events, differences in events grade 2 and higher will be assessed. The event rate and 95% robust confidence interval for each treatment arm will be calculated using a log-linear model for counts using log(person-time) as an offset, treatment as a covariate, assuming a Poisson distribution and using a robust variance (i.e. generalized estimating equations). Event rates will be compared between treatment arms using this same model. Event rates will be compared between treatment arms using this same model and a type I error rate of $\alpha=0.05$ is prespecified. Very rare events will be compared using an exact Poisson test. Additional supporting descriptive safety analyses will be presented.

For Safety OBSP analysis, adverse event follow-up will be censored after the last injection before a termination or a permanent product discontinuation regardless of any delays in injections. If termination or a permanent product discontinuation occurs prior to their first injection, the participant's follow-up time will be censored at the termination or permanent product discontinuation date +1. If termination or a permanent product discontinuation occurs after the first injection, the participants follow-up time will be censored up through 6 weeks after the Week 5 injection, if that is the last injection, or 10 weeks after the last injection for subsequent injections.

7.3.3. Adverse events in Step 1

Objective: To compare the safety of oral CAB vs. oral TDF/FTC in Step 1

Population: Primary Safety

Censoring: AEs are censored at 120 days after randomization for participants who never received an injection; at 1 day after the date of termination or investigational product discontinuation; at date of first injection, whichever occurs first. Reported AEs will be excluded if they occur after the censoring time.

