APPENDIX B - Details of Efficacy Analysis Definitions

Population Definition:

Modified ITT

- Participant is randomized
- Participant is HIV uninfected at randomization (determined by EAC)
- Participant does not have a major enrollment violation – determined by independent adjudication

Note: Only participants with at least one follow-up visit (of any type, including safety and interim visits) with HIV status determined after enrollment will contribute study time to the efficacy analysis.

Censoring for primary efficacy analysis:

- If a study-wide transition to Step 3 occurred, all data from the enrollment visit through the date of transition (plus one month?) will be included
- If no study-wide transition to Step 3 occurred or if the study is stopped early, all ongoing follow-up at the time of decision to stop the blinded portion of the study will be censored on the date of study closure.

Censoring for on blinded study product (OBSP) analysis

Participants will be censored when an injection is delayed, defined as follows:

- **Last non-delayed injection:** The earliest of an injection whose subsequent injection is delayed for the first time (i.e. given >6 weeks after the Week 5 injection or >10 weeks after any other injection) or the last injection before a termination or a permanent product discontinuation
- Follow-up time will be censored at the last visit with HIV status determined up through 6 weeks after the Week 5 injection, if that is the last non-delayed injection, or 10 weeks after the last non-delayed injection for subsequent injections.

Calculation of study time for primary efficacy analysis:

- If HIV infected, study time will be calculated as the number of days between enrollment and the mid-point between first visit where HIV infection was detected and the most recent prior visit where HIV infection was not detectable, as determined by the EAC.
- If HIV uninfected, study time will be calculated as the number of days between enrollment and the last visit with HIV status at or before the censoring time.

Calculation of study time for OBSP analysis:

- If HIV infected prior to OBSP censoring, study time will be calculated as the number of days between enrollment and the mid-point between first visit where HIV infection was detected and the most recent prior visit where HIV infection was not detectable, as determined by the EAC.

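### The Step 2 on-product AE analysis (SAP 7.3.4) borrows an HIV-endpoint censoring rule that, as worded, ends AE follow-up at an HIV-status visit and differs from the Safety OBSP rule in 7.3.2

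*SAP*

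**What the plan says.** Section 7.3.4 aims at safety close to the administration of blinded product, in the Step 2 safety population. For its censoring it says "Details of the OBSP censoring definitions are given in Appendix B", and then "Reported AEs will be excluded if they occur before the first injection or after the OBSP censoring time". The model is carried over from the preceding safety sections, where 7.3.2 specifies a "log-linear model for counts using log(person-time) as an offset".

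Appendix B is headed as efficacy definitions and holds one OBSP censoring rule. Its trigger is a delay: "Participants will be censored when an injection is delayed, defined as follows". Its date is tied to HIV testing: "Follow-up time will be censored at the last visit with HIV status determined up through 6 weeks after the Week 5 injection", or 10 weeks for later injections.

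Section 7.3.2 sets out a separate rule under the label Safety OBSP, and it reads: "adverse event follow-up will be censored after the last injection before a termination or a permanent product discontinuation regardless of any delays in injections". There the cut falls 6 weeks after the Week 5 injection, if that is the last one, or 10 weeks after a later last injection. No HIV visit enters the rule.

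Neither 7.3.4 nor Appendix B says that the appendix rule is adapted for AEs, and the SAP does not state how the two rules relate.

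**The concern.** HIV infection is known only at a test, so ending an infection-free woman's follow-up at her last HIV-status visit is natural for efficacy. An AE has its own onset date and can be reported at a later contact. Ending AE follow-up at an HIV visit therefore discards dated events without need, and discards them from the days after an injection that 7.3.4 is meant to examine.

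The populations differ too. The efficacy analysis that uses Appendix B is restricted by Section 6.5 to women who "had at least one follow-up visit with HIV status determined after the first injection". The Step 2 safety population in 6.7 requires only one injection, so it can include women for whom the appendix rule leaves no time after injection.

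At stake is whether the Step 2 AE table can be reproduced. Two programmers, one working from 7.3.2 and one from 7.3.4, would produce different AE counts and person-time under the same OBSP label.

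**Working it through.** **1. The two rules side by side**

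| | 7.3.2, Safety OBSP | Appendix B, OBSP (used by 7.3.4) |
|---|---|---|
| Qualifying injection | Last before termination or permanent discontinuation | Last non-delayed one, if that comes earlier |
| Delays | Ignored | First delay ends follow-up |
| Cut-off | Full 6 or 10 weeks after it | Last HIV-status visit within those 6 or 10 weeks |
| Start of time | Not stated | Enrollment |

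**2. Days lost to the HIV-visit dating alone**

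Inputs: target days from Appendix A (Step 2 day 0 is the Week 5 injection); limits of 6 × 7 = 42 days after the Week 5 injection and 10 × 7 = 70 days after any other. Assumption: scheduled visits yield an HIV status.

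Loss = limit − days from the qualifying injection to the last HIV-status visit.

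| Last HIV-status visit | After Week 5 injection | After later injections |
|---|---|---|
| Next due injection visit | 42 − 28 = 14 | 70 − 56 = 14 |
| Scheduled visit between injections | 42 − 7 = 35 (Week 6) | 70 − 28 = 42 (Weeks 13, 21); 70 − 7 = 63 (Week 42) |
| The injection visit itself | 42 − 0 = 42 | 70 − 0 = 70 |

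After the Week 185 injection there is no further Step 2 injection visit, so the first row does not apply to it. Off-target or interim visits give values between those shown.

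The loss falls once per woman, at the end of her OBSP time. For scale, the planned average in Steps 1 and 2 is 133 × 7 = 931 days, so 14 days is 14/931 = 1.5% of it and 70 days is 70/931 = 7.5%. For a woman with only the Week 5 injection and no later HIV status it is all 42 days after her injection.

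**3. The difference made by delays**

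Take a woman injected on schedule to day 364 (Week 57), next on day 438 (74 days later, beyond 70), then every 56 days on days 494, 550, 606 and 662. She has no HIV-status visit between days 364 and 438.

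- 7.3.2: 662 + 70 = day 732.
- Appendix B, cut at the HIV-status visit: day 364. Difference 732 − 364 = 368 days and five injections.
- Appendix B, cut at the 10-week limit: 364 + 70 = day 434. Difference 732 − 434 = 298 days.

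Appendix A allows the Week 65 visit up to day 448. After an injection on day 364, one given on days 435 to 448 is therefore inside the visit window but delayed under Appendix B.

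**4. Person-time**

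Appendix B counts study time from enrollment, whereas 7.3.4 excludes AEs before the first injection. Taken together, the roughly five weeks of Step 1 would enter the denominator while its events are kept out of the numerator. If time instead starts at first injection, a woman with only the Week 5 injection and no later HIV status has 0 days, and log(0) is undefined.

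**The case against.** **Two analyses may have two rules.** The rule in 7.3.2 has a branch for women who stop before any injection, so it may serve an analysis of Steps 1 and 2, whereas 7.3.4 covers Step 2 only. The summary of changes in Section 10.1.2 also describes the appendices as covering censoring for efficacy and safety. A first-delay cut may thus be deliberate in 7.3.4. This stands: a reader might infer a flat contradiction between 7.3.2 and 7.3.4, but the SAP does not establish one. It still does not explain dating AE follow-up by an HIV test.

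**Appendix B can be read another way.** Its study-time rule for uninfected women separates the OBSP censoring time from the last HIV-status visit at or before it. On that reading the censoring time is the 6- or 10-week limit, and the losses in step 2 vanish. The censoring block itself, however, places the cut at the visit. The text supports both, and only the handling of delays differs from 7.3.2 on either reading.

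**Undefined offset.** One might infer that the model must fail. It does so only if time starts at first injection, which 7.3.4 does not say. With Appendix B's start the problem becomes a mismatch of events and time.

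**Size.** A loss after every injection might also be inferred, but it occurs once. A woman with no later contact would report few AEs anyway. Section 2.7.3 starts open-label TDF/FTC no later than eight weeks after the last injection visit, so days 56 to 70 can be open-label time for women who transition.

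**7.3.2 is not an obvious default.** Because it ignores delays, it could keep open-label time during pregnancy pauses (Sections 2.7.4 and 4.3) under an on-blinded-product label. This also stands.

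**Conclusion.** Section 7.3.4 does not fix its AE cut-off properly. It relies on a rule built for HIV endpoints whose wording ends AE follow-up at an HIV-status visit, and it leaves the start of person-time unsettled. On the literal reading the cost per woman is 14 days on target dates when the next due visit is her last with HIV status, rising to the whole 42- or 70-day window when none follows. After a first delay the gap from 7.3.2 can be much longer, though that part may be intended.

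These figures assume target visit dates and an HIV status at each scheduled visit attended. The SAP gives no rate of late injections or missed visits, so the total effect cannot be computed. Both arms are injected on the same schedule, so nothing indicates which arm would be favoured. The primary grade 2 or higher comparison is not affected; this is a supplementary safety analysis that should be corrected before its tables are programmed.

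**What to change.** Reconcile 7.3.2, 7.3.4 and Appendix B.

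- In 7.3.4, state that AEs are censored a fixed 6 weeks (Week 5 injection) or 10 weeks (later injections) after the qualifying injection, not at an HIV-status visit, and that AEs and person-time are both counted from first injection to that cut-off.
- State whether the qualifying injection is the last non-delayed one, as in Appendix B, or the last before the woman terminates or permanently discontinues, as in 7.3.2. If the latter, say how open-label time during pregnancy pauses is handled in the analysis.
- Limit the HIV-visit dating in Appendix B to efficacy analyses. If both OBSP rules are kept, give them different names.

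The cost is a few sentences, a label in the appendix and one AE censoring flag. No new data are needed, and visit windows and treatment rules are untouched.

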4.2 Randomization

Participants will be randomized to one of two study arms in a 1:1 ratio. Randomization will be stratified by study site, and a permuted blocks design will be used to ensure balanced treatment assignments within study site. The randomization scheme will be generated, operationalized and maintained by the HPTN Statistics and Data Management Center.

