7. STATISTICAL ANALYSES

7.1 General Analysis Considerations

Any deviations from the original statistical plan will be described in the final report.

7.1.1. *Summary Statistics*

Summary statistics for categorical variables will include frequency and percentage. For continuous variables, number of subjects with non-missing value (n), mean, median, standard deviation (SD), minimum (min), and maximum (max) will be reported. For change from baseline calculations, baseline is defined as Day 0/Randomization visit. If a baseline value is not available from the randomization visit, for certain parameters the baseline value may be obtained from the enrollment visit.

7.1.2. *Visit Windows*

All data will be tabulated per the evaluation visit as recorded on the CRF even if the assessment is outside of the visit window. Visit windows are displayed in Appendix A. In

data listings, the relative day, of all dates will be presented e.g. from date of randomization, or date of last injection.

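### The absolute-value laboratory model leaves out the baseline value and so loses precision on the overall arm difference; the change model also omits it and names no allowance for repeated measurements

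*SAP*

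**What the plan says.** SAP section 7.3.5 (Laboratory evaluations) sets out two formal comparisons for each laboratory outcome.

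- **Model for absolute values.** The core specification is: "A mixed-effects model with participant as the random effect and site and arm as fixed effects will be used to assess overall differences". On the visits used, it states: "Only post baseline visits will be included". Time and time-by-arm terms are added, and skewed outcomes are logged.
- **Model for change.** Here the specification is: "A fixed effect model with site and arm as covariates will be used to assess overall change from baseline for each laboratory outcome". For this model too, "A continuous time (elapsed study time) term and an interaction of time with study arm will be added". No participant effect, correlation structure or robust variance is named.

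Neither list of terms contains the baseline laboratory value. That value is defined in section 7.1.1: "For change from baseline calculations, baseline is defined as Day 0/Randomization visit", with a fallback visit for certain parameters. Section 7.3.5 ends by noting that "Formal comparisons of laboratory values as described above will not be included in the Clinical Study Report"; section 9.2 repeats this.

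**The concern.** A woman's baseline creatinine, ALT or cholesterol would normally predict her later values. The change analysis needs that value, so for women in that analysis it is already in the data set. The absolute-value model does not use it, and between-woman variation that baseline could explain stays in the error of the arm comparison.

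The change model has a different problem. Its elapsed-time term implies several change values per woman, and all of them subtract the same baseline measurement. They are therefore correlated even after the woman's own level cancels. A model with only site, arm and time terms treats them as independent.

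At stake is how well the formal comparisons of continuous laboratory values can be read. Appendix E lists hepatic safety, creatinine, hyperglycaemia and pancreatitis as events of special interest. The two models could give visibly different intervals for the same parameter, one too wide and one too narrow, and section 7.3.5 does not say which governs.

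**Working it through.** **Plan's own figure.** None exists for this point. Section 7.3.5 gives no standard deviation, correlation, interval width or power. The trial's event target concerns HIV infection and does not bear on it.

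**Inputs.** From the SAP: the model terms in 7.3.5 and 1:1 allocation (4.2). Assumed: equal variance σ² at every visit, the same correlation r between any two visits including baseline, m post-baseline visits, and no missing visits. Variances of the overall arm difference are in units of 2σ²/n, with n women per arm.

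**Formulas.**
- Post-baseline only: V = (1 + (m − 1)r)/m
- Baseline as covariate: V − r²
- Change, with a valid variance: V + 1 − 2r = (1 − r)(1 + 1/m)
- Change, rows treated as independent: 2(1 − r)/m

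**Absolute-value model.**

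| m | r | post-only | with baseline | SE ratio | SE cut |
|---|---|---|---|---|---|
| 4 | 0.5 | 0.625 | 0.375 | 0.77 | 23% |
| 4 | 0.7 | 0.775 | 0.285 | 0.61 | 39% |
| 10 | 0.5 | 0.55 | 0.30 | 0.74 | 26% |
| 10 | 0.6 | 0.64 | 0.28 | 0.66 | 34% |
| 10 | 0.7 | 0.73 | 0.24 | 0.57 | 43% |

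At m = 10 and r = 0.6 the variance ratio is 0.28/0.64 = 0.44, which is worth about 1/0.44 = 2.3 times as many women. Over a wider range, r = 0.3 to 0.9, the post-only interval is 1.05 to 2.29 times the adjusted one at m = 1 and 1.12 to 2.89 times at m = 5. The direction is the same at every correlation above zero.

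**Change model as written.** Reported over true variance is [2(1 − r)/m] / [(1 − r)(m + 1)/m] = 2/(m + 1), whatever r is. The reported standard error is therefore √(2/(m + 1)) of the true one: 1.00, 0.71, 0.58 and 0.43 at m = 1, 3, 5 and 10. At m = 5 a nominal 1.96 acts as 1.96 × 0.577 = 1.13, a two-sided false-positive rate of about 26%.

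**Change model with a valid variance.** Only in this case is it inefficient: its interval is 1.24 to 1.03 times the adjusted one at m = 1, and 1.55 to 1.04 times at m = 5, as r goes from 0.3 to 0.9.

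**Simulation** (1,000 runs, 400 per arm, m = 5, r = 0.6, no site effect). Mean standard errors were 0.058 post-only, 0.040 with baseline, 0.049 for change with a valid variance and 0.028 for change as written. The last had a false-positive rate of about 26%. The formulas give √(2 × 0.68/400) = 0.058, √(2 × 0.32/400) = 0.040, √(2 × 0.48/400) = 0.049 and √(2 × 0.16/400) = 0.028. The standard error of the time-by-arm slope was 0.0141 with or without baseline.

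**The case against.** The strongest reply is that this is a matter of efficiency in secondary material. Allocation is randomised, so leaving baseline out of the absolute-value model causes neither bias nor an invalid test. The comparisons stay out of the Clinical Study Report and touch neither primary analysis. The trial is also large. With 3,350/2 = 1,675 women per arm and full follow-up, m = 10 and r = 0.6 give a post-only standard error of √(2 × 0.64/1675) = 0.028 SD. That is 90% power for about 0.09 SD, against about 0.06 SD with baseline. No document shows that this difference matters clinically. All of this stands, and it limits the weight of the point.

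A reader might infer more than the documents support in four ways:

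- **That both models give intervals that are too wide.** The change model as written errs the other way once there are several visits. It merely loses precision if it has one value per woman or is given a valid variance.
- **That these are the only formal comparisons of laboratory safety.** Section 9.1 puts reportable laboratory abnormalities into the adverse event tabulation, and section 7.3.2 formally compares adverse events of grade 2 or higher. The models in 7.3.5 are the formal comparisons of continuous values only.
- **That detection of effects emerging over time suffers.** Under a constant-correlation structure the time-by-arm slope gains essentially nothing from baseline.
- **That a Day 0 value exists for every parameter.** This is only inferred from the planned change analysis. Section 7.1.1 allows another visit for some parameters, and section 9.2 summarises laboratory change from screening.

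The objection does not reach the missing within-woman correlation in the change model. That is a question of validity, and it is out of line with section 7.3.7(c), where weight change is modelled with random person effects.

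**Conclusion.** The point holds for the overall arm difference. The absolute-value model discards usable baseline information. The 23% to 43% figure depends on equal correlation of 0.5 to 0.7 and 4 to 10 visits, none of which the SAP states; the direction needs only a non-zero correlation. Read literally and with several visits per woman, the change model understates its standard error by a factor that depends on the number of visits and not on the correlation, as long as the correlation is equal. If the programmers intended one value per woman or a clustered variance, that fault disappears, but the text does not say so.

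The consequence is limited to the reading of supportive laboratory comparisons. Nothing here puts the efficacy result, the primary safety comparison or the Clinical Study Report in doubt. The correction is worth making mainly because it costs so little.

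**What to change.** In section 7.3.5:

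1. Add the baseline value, as defined in 7.1.1 and on the log scale where the outcome is logged, as a covariate in the absolute-value mixed model. Name the visit that supplies it for each parameter, given the screening reference in 9.2.
2. Either keep change from baseline as description only or, if it is to support inference, add the baseline covariate and a participant random effect or robust variance. With the same scale, covariates and participant term, the two models return the same arm estimate, so little is lost by keeping one.

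The cost is one covariate, one clarified sentence and the matching program change. The downside is that women without a baseline value drop out of a covariate-adjusted model. Modelling baseline as an additional outcome with a mean common to both arms keeps them in, at the price of a slightly more complex specification.
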